### **Aims 2.1 and 2.2 Exclusion Criteria**

1. Serious suicide or homicide risk, as assessed by evaluating clinician
2. Unstable medical illness including cardiovascular, hepatic, renal, respiratory, endocrine, neurologic
3. Substance use disorder active within last six months
4. Psychotic features (current episode or lifetime), as assessed by SCID
5. Laboratory evidence of untreated hypothyroidism
6. If treated hypothyroidism, significant change in levothyroxine dose within the prior three months
7. Use of hormones (estrogens, androgens or related hormones) within the prior three months
8. Any investigational psychotropic drug within the last two weeks
9. In the judgment of the study clinician, unlikely to be able to participate safely throughout the study period (three or more episodes of self-harm in the past year, documented history of poor treatment adherence, or frequent missed appointments ( $>50\%$ ) in the past year)
10. Alanine aminotransferase (ALT) or creatinine  $> 3x$  upper limit of normal.
11. History of a hormone-responsive cancer
12. Receiving strong CYP3A4 inducers or inhibitors or who intend to consume grapefruit products regularly during the study

Briefly describe study procedures. Include any local site restrictions, for example, “Subjects enrolled at Partners will not participate in the pharmacokinetic portion of the study.” Describe study endpoints.

### **Study visits**

#### **Aim 1**

**Screening Visit/ Baseline Visit (n=120):** A “Screening Visit” will be conducted to determine eligibility for the protocol. It is estimated that 120 women will need to be screened to obtain 60 eligible study subjects (20 with treatment-resistant depression, 20 with treatment responsive depression and 20 controls with no depression). The screening visit and baseline visit are simultaneous, and labs will be drawn if the subject passes the psychiatric assessments and qualifies per above criteria. ○ A physical examination, medical history and urine toxicology

- Psychiatric assessments: SCID and MADRS ○ MGH Anti-depressant history form
- If qualified based on psychiatric assessment, blood draw for ALT, creatinine, cbc, thyroid function tests
- Additional aliquots will be drawn for future testing of allopregnanolone and other hormones **Aim 2**

**Screening Visit (n=20):** A screening visit will take place to determine eligibility for enrollment. Participants will be asked to complete the MGH ATRQ and sign release of information forms to request documentation from prescribing clinicians.

Screening visit testing will include:

- Complete medical history ○ Physical examination, including height, weight and vital signs ○ 0800h Blood draw for ALT, AST, bilirubin, creatinine, CBC, thyroid stimulating hormone (TSH) and FSH
- Urine toxicology
- Urine pregnancy test in women <55 years of age ○ Diagnostic interview with SCID ○ MDD symptom assessment with MADRS
- Completion of the MGH ATRQ

If antidepressant-resistance is confirmed following screening procedures, the subject will be scheduled for a baseline visit approximately 1-2 weeks later.

**Baseline Visit for the Ganaxolone Augmentation Study (n=10):** Eligible subjects will undergo baseline testing immediately before the augmentation phase of the protocol.

Baseline visit testing will include the following. However, the safety labs will not be repeated if the Baseline visit occurs within 6 weeks of the screening visit.

- Weight, vital signs, waist-to-hip ratio, and consumptive habits (alcohol, caffeinated beverages) will be recorded.
- Electrocardiogram
- Neuroactive steroid panel, including allopregnanolone, morning blood cortisol, late night salivary cortisol and 8 a.m. salivary cortisol
- Depression efficacy endpoints: MADRS, HAM-D, IDS-SR and SDQ ○ Cognitive Functioning: CPFQ
- Persistent/residual symptom assessment: SF-36, BFI, ESS, FSS, DISF, SFQ, GAD-7 ○ Safety assessments: SAFTEE-SI and CHRT ○ We will distribute the Study Drug Compliance and Hot Flash Diary ○ Cognitive testing (Probabilistic Reward and Pattern Separation Tasks) will be performed

**Follow-up Visits (Ganaxolone Augmentation Phase):** Subjects will then receive Ganaxolone therapy. In the case of a drop out, subjects will be asked to come in for an optional close-out visit. This visit will include all of the week 8 measures. Follow-up visits will take place at weeks 1, 2, 4, 6 and 8 post-baseline.

Follow up visits will include:

- Weight and vital signs will be recorded (weeks 1,2, 4, 6, 8 and 10); electrocardiogram will be performed in any subject with bradycardia (HR<60) or tachycardia (HR>100)
- Waist-to-hip ratio (week 8)
- Depression: MADRS, IDS-SR, CGI-S, CGI-I, SDQ (weeks 2, 4, 6, 8 and 10),

- HAM-D (week 8 only) ○ Cognitive Functioning:
- CPFQ (weeks 2, 4, 6, 8 and 10)
- Persistent/residual symptom assessment: SF-36, BFI, ESS, FSS, DISF, SFQ, GAD-7 (weeks 2, 4, 6, 8 and 10) ○ Safety: SAFTEE-SI, CHRT (weeks 2, 4, 6, 8 and 10) ○ Salivary cortisol (week 8)
- Medication management sessions (weeks 2, 4, 6 and 8) ○ Neuroactive steroid panel (week 8)
- Blood draw for ALT, AST, bilirubin (week 8)
- We will distribute the Study Drug Compliance and Hot Flash Diary (weeks 2, 4, 6, and 8) ○ Cognitive testing (Probabilistic Reward and Pattern Separation Tasks) will be performed (week 8 only)
- Measurement of ganaxolone levels

Taper: After the 8-week visit, subjects receiving [REDACTED]

[REDACTED] A 10-week visit will be performed and will include:

- Vital signs ○ Safety: SAFTEE-SI, CHRT ○ Depression: MADRS, IDS-SR, CGI-I
- Persistent/residual symptom assessment: SF-36, BFI, ESS, FSS, DISF, SFQ, SDQ, GAD-7

**3-Month Follow Up Questionnaires:** Three months after the 10-week visit or last visit completed, subjects will be sent the following questionnaires to complete: ○ IDS-SR, BFI, SDQ, GAD-7

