**Specific Aim 2.1**

**Allopregnanolone analog augmentation improves depressive symptoms in women with treatment-resistant depression.** We will investigate in women with treatment-resistant depression whether allopregnanolone analog augmentation leads to a reduction in depressive symptoms, as measured by the *Montgomery-Asberg Depression Rating Scale* and *Clinical Global Impression-Severity* over an 8-week period. *Note that Aim 2.1 is not dependent on Aim 1, as pharmacologic levels of allopregnanolone could still lead to improvement in depressive symptoms even if the Aim 1 hypothesis that physiologic levels of allopregnanolone are lower in women with treatment-resistant depression is not confirmed.*

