Additionally, we have successfully conducted studies of hormone augmentation strategies in women with treatment-resistant depression and have published a pilot study investigating the effects of low-dose testosterone augmentation on treatment-resistant depression in women, which formed the basis of an ongoing, NIH-funded trial and demonstrated a marked improvement in **Montgomery-Asberg Depression Rating Scale (MADRS)** scores at 2 weeks that was sustained through the 8-week period with administration of low-dose testosterone. At this time, we have recruited more than 50 subjects for an ongoing NIH-funded randomized, double-blind clinical trial of low-dose testosterone for treatment-resistant depression in women in follow-up to this pilot study. We hypothesize that the potential antidepressant effects of low dose testosterone are mediated by neuroactive steroids, including allopregnanolone. Moreover, both the pilot and follow-up studies speak to our ability to recruit and study this specific population of women with treatment-resistant depression.

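### CGI-S is one of two measures named for Aim 2.1, but no pre-treatment rating is scheduled, so its change from baseline to week 8 cannot be computed

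*Protocol*

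**What the plan says.** Specific Aim 2.1 of the protocol asks whether augmentation "leads to a reduction in depressive symptoms, as measured by the" MADRS and CGI-S over 8 weeks. These are the only two scales the aim names.

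The schedule is under Study visits, Aim 2:

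- **Screening.** The only symptom severity scale is given as "MDD symptom assessment with MADRS".
- **Baseline.** This is the pre-treatment reference visit: "Eligible subjects will undergo baseline testing immediately before the augmentation phase of the protocol". The depression battery is "Depression efficacy endpoints: MADRS, HAM-D, IDS-SR and SDQ".
- **Follow-up.** The depression line reads "Depression: MADRS, IDS-SR, CGI-S, CGI-I, SDQ (weeks 2, 4, 6, 8 and 10". This is the first place CGI-S appears.
- **Week 10.** A separate list for this visit gives MADRS, IDS-SR and CGI-I, without CGI-S.

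The SAP consists of a sample-size statement based on MADRS (10.7 points, SD 7.5, n=10). It does not mention CGI-S.

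**The concern.** A reduction over 8 weeks needs a value at the start of the 8 weeks. CGI-S rates current severity, so a week-8 score alone does not show whether a woman has improved.

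This matters more here than it would in a controlled trial. The protocol describes no comparison group for Aim 2.1: ten women all receive ganaxolone, and change within each woman is the only efficacy contrast. Two randomised arms could at least be compared on week-8 CGI-S without a baseline. A single arm cannot.

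The SAP also says the study is meant to supply an effect size for later funding applications. No baseline-to-week-8 CGI-S effect could be supplied.

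**Working it through.** The plan states no figure for CGI-S, so there is none to reproduce. The check sets the aim beside each Aim 2 visit list in the protocol.

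| Visit | MADRS | CGI-S |
|---|---|---|
| Screening | yes | no |
| Baseline (before first dose) | yes | **no** |
| Week 1 | no | no |
| Weeks 2, 4, 6, 8 | yes | yes |
| Week 10, follow-up list | yes | yes |
| Week 10, separate list | yes | no |
| 3-month questionnaires | no | no |

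**Counts.** Scheduled CGI-S ratings before treatment: 0. Scheduled CGI-S ratings on treatment through week 8: 4 (weeks 2, 4, 6 and 8). A baseline-to-week-8 CGI-S change is therefore available for 0 of 10 women. The same change in MADRS is scheduled for all 10.

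**Is it hidden elsewhere?** The remaining baseline instruments are CPFQ, SF-36, BFI, ESS, FSS, DISF, SFQ, GAD-7, SAFTEE-SI and CHRT, plus physical measures, ECG, steroid and cortisol samples and cognitive tasks. None is CGI-S. These lists show no redaction.

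**Does it look deliberate?** Every other repeated scale of current status in the follow-up list has a baseline value: MADRS, IDS-SR, SDQ, HAM-D, CPFQ, SF-36, BFI, ESS, FSS, DISF, SFQ, GAD-7, SAFTEE-SI and CHRT. CGI-I has none because it rates improvement. CGI-S is the one status scale left out, although Aim 2.1 names it. HAM-D, IDS-SR and SDQ, which the aim does not name, are all collected at baseline. This reads as an omission.

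**Would week 2 serve as the reference?** For each woman,

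change(0 to 8) = change(0 to 2) + change(2 to 8).

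The schedule supplies only the second term, which covers 8 − 2 = 6 of the 8 weeks. The first term is unobserved. It includes the start of treatment and the week-1 dose decision described under Drug Safety. The protocol's Background says the group's testosterone pilot showed marked improvement in MADRS "scores at 2 weeks that was sustained through the 8-week period". If CGI-S on ganaxolone followed that pattern, most of the change would fall in the missing term, and the week-2-to-8 change could be near zero even with a working drug. That pilot used a different drug and a different scale, and no week-2 figure is given, so this shows the risk and does not estimate its size.

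**Early leavers.** The optional close-out visit repeats the week-8 measures. A woman who left before week 2 and attended it would have a CGI-S score with nothing to compare it with.

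**The case against.** **The visit lists are not exhaustive.** The protocol requires the Beck Suicide Index at every visit, yet no visit list contains it. It requires blood draws at all visits except weeks 1 and 10, while the follow-up list dates its draws only to week 8. The baseline list is introduced as what testing will include, which does not forbid more. CGI-S might therefore be rated in practice. This does not rescue the plan: the Beck index and the blood draws are required by other text, and a baseline CGI-S is required by none.

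**MADRS carries the study.** Eligibility, reassessment and the sample size all rest on MADRS, which is scheduled at baseline and week 8. Aim 2.1 does not call the two scales co-primary or give them weights. This stands: Aim 2.1 can still be tested on the measure the study was sized on. It does not make the other named measure evaluable.

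**Other information exists.** The four on-treatment CGI-S ratings allow a week-2-to-8 trajectory and a description of severity at week 8. CGI-I is collected from week 2, and HAM-D and IDS-SR have baseline and week-8 values. This limits the loss of information about improvement in general. But CGI-I is a different rating that Aim 2.1 does not name, and none of these gives a CGI-S change over the 8 weeks.

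**The aim does not literally say change from baseline.** Its wording is "as measured by the *Montgomery-Asberg Depression Rating Scale* and *Clinical Global Impression-Severity* over an 8-week period". With the first rating at week 2, however, a reduction across all 8 weeks cannot be measured under any reading.

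**Conclusion.** The concern holds. The aim and the schedule contradict each other: CGI-S reduction over 8 weeks is a named outcome, and the schedule provides no pre-treatment value for it. Followed exactly, the plan yields a baseline-to-week-8 CGI-S change for 0 of 10 women, and neither the protocol nor the SAP defines another reference time.

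The conclusion assumes only that the schedule is carried out as written, with no unscheduled rating. How much response a week-2 reference would miss is unknown. The MADRS result and its sample-size basis are untouched. The week-10 disagreement about CGI-S is a separate, minor inconsistency outside the 8-week outcome and adds no weight here.

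This should be corrected before dosing, because a missed pre-treatment rating cannot be obtained later.

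**What to change.** 1. Add CGI-S to the list for the Baseline Visit for the Ganaxolone Augmentation Study, rated before the first dose, ideally by the clinician who rates the baseline MADRS.
2. State in Specific Aim 2.1 and in the SAP that the CGI-S outcome is change from baseline to week 8.
3. Make the two week-10 lists agree on whether CGI-S is rated there.
4. For any woman already treated without a baseline rating, record it as missing and report her on-treatment CGI-S descriptively. Do not rate baseline severity retrospectively or substitute week 2 without saying so.

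The cost is one clinician rating per woman (ten in all) at a visit that already takes place, plus a short amendment. If the rating is not added, Aim 2.1 should name MADRS alone as the measure of reduction and describe CGI-S as an on-treatment severity rating.

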### **Blood collection**

#### **Aim 1**

154 mL of blood will be drawn at the one study visit for Aim 1

#### **Aim 2**

Subjects will complete a blood draw at all study visits except the week 1 and week 10 visits. This will total 526mL of blood over the approximate 10-week study period from screening to the final visit

For studies involving treatment or diagnosis, provide information about standard of care at Partners (e.g., BWH, MGH) and indicate how the study procedures differ from standard care. Provide information on available alternative treatments, procedures, or methods of diagnosis.

Subjects being studied in this protocol will still have at least moderate depression. Standard care alternatives are presented in the Consent form. Subjects at MGH are offered three months of free medication management clinic services for depression treatment after completion of a clinical trial such as this one. Research staff will assist in arranging subsequent treatment by providing referrals and communications to subsequent providers.

Describe how risks to subjects are minimized, for example, by using procedures which are consistent with sound research design and which do not unnecessarily expose subjects to risk or by using procedures already being performed on the subject for diagnostic or treatment purposes.

The procedures to protect against or minimize potential risks include the following: (1) the assignment of unique study subject numbers to patients, (2) the use of these primary identifiers throughout the study, (3) storage of information in locked file cabinets, and (4) access limited to study personnel for these file cabinets and data.

We have set up exclusion criteria to minimize risks:

- Subjects must be medically stable as defined in this protocol.
- We exclude people who may be considered particularly vulnerable in clinical trials, including those at acute risk for suicide, those with active substance abuse or dependence, and those with psychosis (or treated with antipsychotic medications).
- Because we are investigating the efficacy of a hormone, it will be important to exclude patients with other endocrine abnormalities which could contribute to treatment resistance or with a changing endocrine status.

Study Subjects will be discontinued from the study if they:

- a. Score a 6 or 7 on the CGI-I on 2 consecutive study visits

Describe explicitly the methods for ensuring the safety of subjects. Provide objective criteria for removing a subject from the study, for example, objective criteria for worsening disease/lack of improvement and/or unacceptable adverse events. The inclusion of objective drop criteria is especially important in studies designed with placebo control groups.

**Suicide Prevention:** Suicidal ideation will be assessed by the Beck Suicide Index at each visit. Patients who develop active suicidal ideation, or who are felt by the study clinician to be at high risk for suicide, will be discontinued from the study and referred for hospitalization and further treatment if clinically indicated. In addition, each study subject will be extensively interviewed at each study visit by a highly trained psychiatrist, who not only has extensive experience in the treatment of major depression, but also with these issues in the setting of clinical trial protocols. Patients in research protocols have much more access to psychiatrists than patients in the community, as a study psychiatrist is available by pager 24 hours per day. Moreover, the studies are performed in hospitals in which patients can be immediately admitted, if necessary to ensure safety.

### **Drug Safety:**

Women with treatment-resistant depression will be administered Ganaxolone (████████). A determination will be made at the one-week visit as to whether the Ganaxolone dose will be escalated ██████████. This will be based on tolerability and absence of side effects, including the presence of sedation and dizziness, which will be specifically asked about. The dose will not be escalated if a subject has experienced either of these – or other significant side effects. Rather, such subjects will be maintained on the lower dose ██████████. Subjects receiving ██████████ who experience daytime drowsiness may be subsequently reduced ██████████. If drowsiness continues on this lower dose, the dose will be reduced ██████████.

[REDACTED]. A phone call will be made to each subject in whom a dose adjustment is made one week after the dose adjustment to determine if the subject continues to experience continuing side effects. Subjects will be advised to take Ganaxolone with food to maximize medication absorption and to avoid alcohol. In person psychiatric reassessment will occur at 2, 4, 6, 8 and 10 weeks with MADRS. Close monitoring of patients throughout the study will ensure that adverse effects from treatment, exacerbation of symptoms, or emergence of suicidality, mania or psychosis will be promptly recognized so that patients can be treated appropriately. All patients will be instructed on how to contact study clinicians in the case of an emergency. They will also be instructed on how to contact the Acute Psychiatry Service (APS) at MGH, which provides

emergent psychiatric care on a 24h/day basis. They will additionally be offered 3 months of psychiatric follow up through the [REDACTED] if desired.

Every effort will be made to keep patients in the study. Acceptable reasons for early discontinuation include: 1) request of patient, 2) decision of physician, 3) serious adverse event, 4) worsening of depression requiring hospitalization, 5) emergence of hypomania, mania or psychotic symptoms.

A Data Safety Monitoring Board will review safety data, including adverse events, twice-a-year and will be available in the interim to consider any urgent matters.

[REDACTED]

[REDACTED]

**Risks of blood sampling:** Blood sampling is performed in the study, and there is always a very minor risk of infection, bruising, or syncope during a blood draw. There is also the discomfort of having one's blood drawn.

**Discomforts with Questionnaires:** Answering detailed questionnaires may create some inconvenience for subjects.

[REDACTED]

[REDACTED]

Treatment-Resistant Depression Augmentation  
Therapy with An Analog of the Neuroactive Steroid  
Allopregnanolone: A Pilot Study

NCT02900092

Version Date: 11/8/18

**Determination of an n=10 women with treatment-resistant depression:** Based on our pilot data of the effect of low-dose testosterone on depression severity in nine women with treatment-resistant depression in which there was an effect size of 10.7 points on the MADRS with an SD 7.5, we will have ample power to detect a clinically significant effect size with the proposed sample size. The data from this study will provide an effect size for power calculations for applications for further funding.
